Condition:	Fertility disorders
Objectives:	To compare the total number of metaphase II (MII) oocytes between the two groups
Investigational Product:	Elonva , Puregon
Interventions:	A single injection of 150mcg of corifollitropin alfa will be administered at day 2/3 of the cycle, followed by 225IU of recombinant FSH (rFSH) in a fixed antagonist protocol. Cycle monitoring will be performed through serum estradiol (E2), progesterone and luteinizing hormone (LH) assessments, and serial transvaginal ultrasound examinations. The study will include exclusively patients with ≤ 9 follicles ≥ 11 mm on the day of triggering. Therefore, patients will be randomly allocated in two groups: Group A (control group) will undergo conventional triggering with hCG 5000 IU and a single oocyte retrieval (OR) will be performed 36 hours later; Group B (study group) will undergo triggering with GnRHa 0,2ml and a first OR will be performed 36 hours later. In both groups, triggering will be formed if two or more follicles ≥ 17 mm are observed and all follicles >10 mm will be aspirated, in line with current clinical practice (Nivet et al., 2016). In Group

	
B (study group), 225 IU of rFSH will continue after the first trigger. Antagonist administration will be initiated when at least one follicle measuring ≥ 14 mm will be present in the ultrasound. If one or more follicles ≥ 17 mm are observed, patients will undergo a second triggering with hCG 5000 IU and a second OR will be performed. In case of patients with no follicular development following 13 additional days of rFSH, the cycle will be cancelled. Metaphase II (MII) oocytes will then be injected according to standard ICSI procedure. In the control group a fresh single/double embryo transfer will be performed according to clinical practice (day 3 or day 5). For the study group, a freeze-all strategy will be applied, followed by a transfer of a maximum two embryos in an artificially prepared frozen-thawed cycle.

Endpoints:	
 Number of MII oocytes Number of COCs Number of preovulatory follicles Number of oocytes fertilized Number of available embryos and their quality Duration of stimulation Total dose of gonadotropins administered Clinical pregnancy and live birth rates of the first frozen cycle Cumulative live birth rates
Study population:	Infertile patients
Number of patients:	46
Overview of study design:	Single center randomized superiority pilot study
Statistical Considerations:	Our sample size of 46 patients (23 per group) has a power of at least 90% to detect superiority of the double trigger group (mean 5.4 MII) versus control group (mean 3.4 MII), standard deviation (SD=2), using a two-sided, t test, at significance level alpha of 0.05
Sponsor:	UZ Brussel
Country(ies) of Recruitment:	Belgium
Inclusion Criteria:	
 Age ≥ 25 - ≤ 40 BMI ≤ 35 and ≥ 19

	
 • Antimüllerian hormone (AMH) level of ≤ 1.5 ng/mL or antral follicular count of ≤ 6 follicles or ≤ 5 oocytes retrieved in a previous cycle following standard conventional ovarian stimulation. • Normal basal ultrasound < 6 months before the start of the treatment (presence of uterus and two ovaries without proof of abnormalities) • Signed informed consent
Exclusion Criteria:	
 • Testicular sperm extraction • History of > 3 three consecutive previous unsuccessful IVF cycles • Use of oral contraceptives < 3 months before start of the treatment • PCOS according to the Rotterdam criteria • Ovarian stimulation for pre-implantation genetic testing (PGT-A/M) • Medical/social freezing • History of untreated autoimmune, endocrine or metabolic disorders • Ovarian cystectomy or oophorectomy • Patients will be allowed to participate in the study only once.
Date of first enrolment:	September 2019
Target sample size:	46

3. Protocol Version History

Version No.	Approval Date Lead EC	Release Date
1.0		

4. Sponsor/Coordinating Investigator Information

Coordinating Investigator: [name]. [name]

Sponsor: UZ Brussel

Principal Investigator: [name]. [name]

Co-investigators: [name]. [name], [name]

Statistician: [name]. [name]

Laboratory: UZ Brussel

Pharmacy: UZ Brussel

Study Coordinator: [name], CRG UZ Brussel

Study sites and co-investigators: CRG-UZ Brussel

5. List of Abbreviations

ADR	Adverse drug reaction
AMH	Anti-müllerian hormone
ART	Assisted reproductive technologies
BMI	Body mass index
CI 95%	Confidence Interval 95%
CC	Cumulus cells

CO C	Cumulus oocyte complexes
CO H	Controlled ovarian hyperstimulation
E 2	Oestradiol
h CG	Human chorionic gonadotropin
FF	Follicular fluid
FS H	Follicle stimulating hormone
Gn RH	Gonadotropin releasing hormone
I U	International units
Inf ertility	The incapacity to conceive after 12 months of unprotected intercourse
IV F/ICSI	In vitro fertilization/Intra-cytoplasmic sperm injection
IV M	In vitro maturation
L H	Luteinizing hormone
M II	Metaphase II oocytes
OH SS	Ovarian hyperstimulation syndrome
OR /OPU	Oocyte retrieval/ovum pick up
PGT -A/M	Pre-implantation genetic testing for aneuploidy/monogenic disorders
R CT	Randomised Controlled Trial
r FSH	Recombinant follicle stimulating hormone

6. Introduction

Controlled ovarian hyperstimulation (COH) has been established as a prerequisite in assisted reproduction technologies (ART), as it induces multifollicular development, resulting in a higher number of oocytes retrieved. The rationale is that an increase in the number of oocytes harvested could yield more available embryos, providing higher cumulative live birth rates in infertile patients (Drakopoulos et al., 2016).

On the other hand, multiple major and minor waves in follicular development have been described during the intraovulatory period of healthy women (Baerwald et al., 2003). It seems plausible that ovarian stimulation does not take full advantage of the whole follicular cohort as even small folli

cles (10-14 mm in the study by Nivet et al (Nivet et al., 2016); 8-12 mm in the study by Wirleitner et al (Wirleitner et al., 2018) have been shown to produce transferable embryos and viable pregnancies (Nivet et al., 2016; Wirleitner et al., 2018).

However, aspiration of small follicles may not be the optimal strategy to take full advantage of the whole follicular cohort: in fact, aspiration of small follicles yields significantly lower oocyte recovery rates and proportion of transferable embryos compared with medium and large follicles (Nivet et al., 2016).

Thus, prolonging COH after the first ovarian aspiration and performing a second egg retrieval when small follicles have reached a medium/large size might increase the number of oocytes harvested and provide more available embryos.

7. Study Schematic and Schedule of Activities

7.1 Study Schematic

This is a prospective superiority randomized pilot study which will be performed at UZ Brussel

7.2 Study Activities

The total duration of the study will be approximately 1.5 years

The duration of treatments is per investigators' judgment.

Number of patients included: A total number of 46 women will be analyzed

8. Study Objectives and endpoints

8.1 Primary Objective

The primary objective measure will be to compare the total number of metaphase II (MII) oocytes between the two groups.

8.2 Secondary Objectives

Secondary objectives will be to compare the total number of available embryos, number of cumulus oocyte complexes (COCs) retrieved, number of oocytes fertilized, duration of stimulation, total dose of gonadotropins administered, clinical pregnancy and live birth rates of the first frozen cycle and cumulative live birth rates (defined as the first live birth following the transfer of fresh and subsequent frozen-thawed embryos) between the two groups. A cost-effectiveness analysis will be performed in case of superiority of the double trigger group.

- Number of MIIs
- Number of COCs
- Number of available embryos
- Number of oocytes fertilized
- Duration of stimulation
- Total dose of gonadotropins administered
- Clinical pregnancy and live birth rates of the first frozen cycle
- Cumulative live birth rates

9. Investigational Plan

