11.2 Randomization

This is a prospective superiority randomized pilot study. Patients will be randomized to either control group (Group A) or double trigger group (Group B), on the day of triggering, only after patient eligibility has been established and patient consent has been obtained. Randomization sequence and allocation will be created using a computer-generated randomization list, using 1:1 allocation.

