12.1 Treatments Administered

A single injection of 150mcg of corifollitropin alfa will be administrated at day 2/3 of the cycle, followed by 225IU of recombinant FSH (rFSH) in a fixed antagonist protocol. Cycle monitoring will be performed through serum estradiol (E2), progesterone and luteinizing hormone (LH) assessments, and serial transvaginal ultrasound examinations. The study will include exclusively patients with ≤ 9 follicles ≥ 11 mm on the day of triggering. Therefore, patients will be randomly allocated in two groups: Group A (control group) will undergo conventional triggering with hCG 5000 IU and a single oocyte retrieval (OR) will be performed 36 hours later; Group B (study group) will undergo triggering with GnRHa 0,2ml and a first OR will be performed 36 hours later. In both groups, triggering will be performed if two or more follicles ≥ 17 mm are observed and all follicles >10 mm will be aspirated, in line with current clinical practice (Nivet et al., 2016). In Group B (study group), 225 IU of rFSH will continue after the first trigger. Antagonist administration will be initiated when at least one follicle measuring ≥ 14 mm will be present in the ultrasound. If one or more follicles ≥ 17 mm are observed, patients will undergo a second triggering with hCG 5000 IU and a second OR will be performed. In case of patients with no follicular development following 13 additional days of rFSH, the cycle will be cancelled. Metaphase II (MII) oocytes will then be injected according to standard ICSI procedure. In the control group a fresh single/double embryo transfer will be performed

according to clinical practice (day 3 or day 5). For the study group, a freeze-all strategy will be applied, followed by a transfer of a maximum two embryos in an artificially prepared frozen-thawed cycle (overview of all procedures: tables and figures, fig.2).

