16.5 Conflict of Interest

There are no conflicts of interest to declare.

17. Finance and Insurance

If the patient will decide to take part in this study, this will not involve any extra costs for her or her insurer. The additional costs of the study (extra medication for prolonged stimulation, ovum pick-up, additional sampling) will be covered by funding from MSD.

Any participation in a clinical study involves a risk, however small it is. Even if there is no fault, the investigator accepts responsibility for damage caused to the participant (or in the event of death, his/her dependents) and directly or indirectly linked to his/her participation in the study. The sponsor has taken out insurance for this responsibility.

18. Reporting and Dissemination

Missing efficacy and safety outcomes will be considered as negative, regardless of the cause which may justify the lack of said information (e.g. cycle cancelled due to the survival after warming of no embryo or loss to follow-up). These patients will be included in the analysis following the ITT principle.

19. Conflict of interest statement

This study is financially supported by MSD.

None of the other investigators have conflict of interest to declare.

20. Tables and Figures

Fig. 1 study design

[figure not shown]

Table 1: Summarizing table of all investigations and procedures

Group A (control group)

	Day 2 of the cycle	Day 8 of the stimulation	Every 1 or 2 days	Final maturation trigger	Ovum pick-up*	Day 3 or 5 after egg retrieval	12 days after embryo transfer
Informed consent	x						
Inclusion/exclusion criteria	x			x			
Infertility/menstrual/reproductive history	x						
Blood sample for endocrine monitoring (LH, FSH, estradiol, progesteron)	x	x	x		x		
Ultrasound with follicle measurement		x	x				
Embryo transfer						x	
Blood sample for pregnancy hormone (hCG)							x

(*) with collection of follicular fluid and cumulus cells

	Day 2 of the cycle	Day 8 of the stimulation	Every 1 or 2 days	Final maturation trigger	1 st Ovum pick-up* with freezing of all embryos	4 days after first pick-up and 3-4 times after that	2 nd Ovum pick-up* with freezing of all embryos	In the next cycle
Informed consent	x							
Inclusion/exclusion criteria	x			x				
Infertility/menstrual/reproductive history	x							
Blood sample for endocrine monitoring (LH, FSH, estradiol, progesteron)	x	x	x		x	x	x	
Ultrasound with follicle measurement		x	x			x		
Embryo transfer								x

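### Total stimulation duration and gonadotropin dose are compared between arms although Group A's values are in effect fixed before randomisation, so the test is nearly foregone and the extra burden is estimated with avoidable noise

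*Combined protocol and SAP*

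**What the plan says.** Section 8.2 says the secondary objectives are to compare several quantities between the two groups, among them "duration of stimulation, total dose of gonadotropins administered, clinical pregnancy and live birth rates". The Endpoints entry of section 2 also lists duration of stimulation and total gonadotropin dose. Neither place divides them into a part before and a part after allocation. Section 15.3 makes all tests two-sided at p<0.05, with Mann-Whitney for continuous data that are not normal; the t test is named in the sample-size paragraph.

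On timing, section 11.2 states: "Patients will be randomized to either control group (Group A) or double trigger group (Group B), on the day of triggering". Section 12.3 repeats this. By then stimulation has produced the follicles required for triggering and the eligibility count has been made: "The study will include exclusively patients with ≤ 9 follicles ≥ 11 mm on the day of triggering" (section 12.1).

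After allocation the arms differ as follows (section 12.1):

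- Group A: "Group A (control group) will undergo conventional triggering with hCG 5000 IU and a single oocyte retrieval (OR) will be performed 36 hours later". No further FSH is described.
- Group B: "225 IU of rFSH will continue after the first trigger". The second wave ends on response ("If one or more follicles ≥ 17 mm are observed, patients will undergo a second triggering with hCG 5000 IU") or by cancellation if there is no follicular development after 13 additional days.

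Table 1 in section 20 places Group B's next checks at "4 days after first pick-up and 3-4 times after that".

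**The concern.** An outcome compared between randomised arms should be something that allocation can change in either arm. Here, Group A's duration and dose are already set when the woman is allocated, apart from any FSH given on the trigger day itself, on which the documents are silent. Group B's values are the same kind of first-wave quantity plus an amount that cannot be negative.

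Two things follow. The null hypothesis of equal totals is hardly in doubt, so a significant p-value would tell readers almost nothing. And the quantity they need, the additional days and IU the strategy costs a woman, is estimated through a difference of totals. That difference carries first-wave variation from both arms, which allocation cannot influence.

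**Working it through.** **The plan's own figure.** For the primary endpoint the plan gives 23 per arm, means 5.4 and 3.4, SD 2, two-sided 0.05. Noncentrality = 2 / (2 × √(2/23)) = 3.39 on 44 df, and exact t power is 91.2%. The stated power of at least 90% reproduces. Nothing below touches it.

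**Inputs.** From the documents: 23 per arm; 225 IU rFSH per additional day in Group B; first Group B check about 36 h + 4 days = 5.5 days after the first trigger. The documents give no mean or SD for duration and no expected number of extra days. Those are assumptions, varied below.

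**Structure.** Let W be a woman's first-wave days and E her additional days. Group A total = W. Group B total = W + E, with E ≥ 0. W precedes randomisation, so its expectation is the same in both arms. The expected difference in totals is therefore the mean of E in Group B. Estimating that mean directly targets the same effect.

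**How foregone is the test?**

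- Assumptions: first-wave mean 10 days, SD 1, 2 or 3; extra days uniform on 4-6 (all women) or on 5-13 with 0, 20 or 40% of Group B receiving none. In 20,000 simulated trials per case the t test rejected in 98-100%; Mann-Whitney (1,000 trials per case) rejected in 94-100%.
- A wider grid used first-wave SD 1-3, extra days averaging 5 or 9, and 0-40% with no second wave. The t test rejected in at least 95% of trials in 17 of 18 cases and in about 82% in the last.
- The 82% case by hand (SD 3, extra days uniform on 4-6, 40% with none): mean E = 0.6 × 5 = 3.0; variance of E = 0.6 × 25.33 − 9 = 6.2; SE = √((9 + 9 + 6.2)/23) = 1.03; ratio 3.0/1.03 = 2.9; power about 82%.

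**How much precision is lost?** Assume first-wave SD 2 and E drawn from a normal with mean 9 and SD 2.5, clipped to 5.5-13. After clipping, the mean is 9.03 and the SD 2.20.

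- Difference in totals: width = 2 × 2.015 × √((4 + 4 + 4.85)/23) = 3.0 days.
- Mean of E directly: width = 2 × 2.074 × 2.20/√23 = 1.9 days.

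Now let 40% of Group B have no second wave. Mean E = 0.6 × 9.03 = 5.42; variance = 0.6 × (4.85 + 81.5) − 29.4 = 22.4; SD = 4.74.

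- Difference in totals: 2 × 2.015 × √((4 + 4 + 22.4)/23) = 4.6 days.
- Direct: 2 × 2.074 × 4.74/√23 = 4.1 days.

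The gain remains but is much smaller.

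**First-wave noise on its own.** SE = SD × √(2/23) gives 0.29, 0.59 and 0.88 days for SD 1, 2 and 3. The 95% ranges are ±0.58, ±1.16 and ±1.73 days, or about ±130, ±260 and ±390 IU at 225 IU per day.

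**Dose.** Each additional day adds 225 IU: 5 days is 1125 IU and 8 days is 1800 IU. The number of days is not fixed by the protocol.

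**The case against.** The strongest reply is that comparing burden between arms is useful. Only the direction is fixed; the size depends on each woman's second-wave response and on cancellation. In the first set of simulations the mean difference ran from 5.0 to 9.0 days. Section 8.2 also foresees a cost-effectiveness analysis if the double trigger is superior, and total dose per arm is a natural input. All of this stands. It is a reason to estimate the size well and to keep the totals on display, but it does not rescue the significance test.

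It is also fair to say that these are secondary outcomes in a 46-woman pilot, and that the SDs and extra-day distributions above are assumed.

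A reader might infer more than the documents support:

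- **That the comparison merely restates the protocol, with significance guaranteed.** The size is not known in advance, and rejection falls to about 82% in the most extreme case.
- **That chance first-wave imbalance would bias the result.** It is ordinary sampling error, already allowed for in the test and CI.
- **That preovulatory follicle count has the same fault.** "Number of preovulatory follicles" appears only in section 2, with no size threshold, time point or rule for combining waves. It is complete at allocation in Group A only if taken from the trigger-day scan, which the documents do not say; section 13.1.6 measures aspirated follicles at retrieval. It is not part of this point.
- **That 13 days, hence 13 × 225 = 2925 IU, is a documented ceiling.** The 13-day rule in section 12.1 concerns women with no follicular development and states no cap for the others.

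**Conclusion.** The point holds for duration of stimulation and total gonadotropin dose only. That Group A's values are in effect fixed at allocation, and that Group B can only add to them, follows from sections 11.2, 12.1 and 12.3 without any assumption beyond treatment as planned and the unspecified trigger-day dose. The near-certain rejection and the loss of precision (3.0 against 1.9 days in the worked case, 4.6 against 4.1 when 40% have no second wave) rest on the assumed inputs. The consequence is an uninformative p-value and a wider interval than necessary. There is no bias, and the primary comparison, its power and N=46 stand as planned.

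**What to change.** Amend sections 2, 8.2 and 15.3 as follows:

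1. Report duration and dose up to the first trigger as baseline characteristics in both arms, untested. State on which side of the cut any trigger-day dose is counted, with the same rule in both arms.
2. Make the secondary estimate the additional days and IU after randomisation in Group B (zero by design in Group A), with a 95% CI. Keep every randomised Group B woman, entering those with no second wave at what they actually received.
3. Show total duration and dose per arm descriptively, also for use in the cost-effectiveness analysis, without a superiority p-value.

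The cost is wording. Trigger dates, doses and scans should already be available from cycle monitoring, and no visit or patient is added. The downside is the loss of two listed p-values.

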13.1.4 Follow-Up

Follow-up in case of pregnancy will be planned until 7-8 weeks of amenorrhea. From that moment patients are referred to their treating obstetrician. Information on the pregnancy and delivery will be collected once available.

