15.3 Statistical Considerations and Data Analysis

Analyses were performed in intent-to-treat fashion and per-protocol. Consequently, in the intention-to-treat analysis, all patients will be included in the final analysis as long as after fulfillment of the inclusion criteria they were randomly allocated to one of the treatment groups, whereas the per-protocol analysis will include only those patients who completed the treatment originally allocated. Continuous data will be presented as mean \pm SD or median [range] and categorical data will be described by number of cases, including numerator and denominator, and percentages, in line with the CONSORT statement (www.consort-statement.org). Categorical data and continuous data that do not show a normal distribution will be analyzed by Pearson's χ^2 test/Fisher exact test or Mann-Whitney's U test as appropriate.

The normality of the distributions will be assessed with Kolmogorov-Smirnov's test and graphical methods. All tests will be two-sided. Differences will be considered as statistically significant if the null hypothesis could be rejected with $>95\%$ confidence ($p<0.05$). All tests will be performed with the STATA version 13.

Power/Sample Size:

Our sample size of 46 patients (23 per group) has a power of at least 90% to detect superiority of the double trigger group (mean 5.4 MII) versus control group (mean 3.4 MII), standard deviation ($SD=2$), using a two-sided, t test, at significance level alpha of 0.05.

16. Ethical Considerations

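### The first-frozen-cycle pregnancy and live birth endpoint is the first transfer in Group B but a later one in Group A, so the planned between-group comparison is not like-for-like

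*Combined protocol and SAP*

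**What the plan says.** The endpoint list in section 2 includes "Clinical pregnancy and live birth rates of the first frozen cycle". Section 8.2 makes "clinical pregnancy and live birth rates of the first frozen cycle" a secondary objective, to be compared between the two groups. The same section separately lists "cumulative live birth rates (defined as the first live birth following the transfer of fresh and subsequent frozen-thawed embryos".

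Section 12.1 gives the transfer plan. For Group A: "In the control group a fresh single/double embryo transfer will be performed", on day 3 or day 5. For Group B, all embryos are frozen, "followed by a transfer of a maximum two embryos in an artificially prepared frozen-thawed cycle".

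Three general rules could bear on the denominator:

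- Section 15.3, intention to treat: "in the intention-to-treat analysis, all patients will be included in the final analysis", provided they met the inclusion criteria and were randomised.
- Section 15.3, per protocol: "the per-protocol analysis will include only those patients who completed the treatment originally allocated".
- Section 18: missing efficacy and safety outcomes count as negative whatever the cause. The examples are a cycle cancelled because no embryo survived warming, and loss to follow-up.

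Section 13.1.4 says of follow-up: "Information on the pregnancy and delivery will be collected once available".

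**The concern.** One label covers two different events. In Group B the first frozen cycle is the first chance of pregnancy. In Group A it is at best the second, reached only by women with embryos left after the fresh transfer and, in the usual sequence, only if that transfer failed.

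The denominator is not stated, and each candidate has a fault:

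- **All randomised women.** Randomisation is preserved, but a Group A woman who delivers after her fresh transfer adds nothing to the numerator. Group A is marked down for succeeding early.
- **Women who reach a frozen cycle.** Entry depends on events after randomisation that differ by group, and Group A contributes few women. The direction of any bias is uncertain.

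An apparent benefit of double triggering on pregnancy or birth could therefore come from the definition alone, and the denominator could be chosen after the data are seen. Cumulative live birth provides a fair comparison for live birth. Clinical pregnancy has no cumulative counterpart in the plan.

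**Working it through.** The plan states no expected rate or power for this endpoint. Its 90% power claim concerns MII oocytes and does not bear on this point.

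**1. Do the general rules settle the denominator?** A Group A woman who delivers after a fresh transfer has a known outcome. Her frozen cycle is not applicable rather than missing, and the section 18 examples do not describe her. The per-protocol rule does not help, because she can complete her allocated treatment without any frozen cycle. No section says how she scores.

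**2. Direction, all randomised women counted.** Let N be the number of usable embryos per woman, with the same distribution in both groups, and q the live birth probability per embryo. With single transfers:

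- Group B: q × P(N≥1)
- Group A, frozen cycle only after a failed fresh transfer: q × (1−q) × P(N≥2)
- Group A, every woman with surplus embryos has a frozen cycle: q × P(N≥2)
- True first-transfer rate, both groups: q × P(N≥1)

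P(N≥2) cannot exceed P(N≥1), so A is lower than B whenever some women have exactly one usable embryo, or frozen cycles follow only failures.

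**3. Size, on assumed inputs.** None of these inputs is in the documents. N is negative binomial (Poisson with gamma heterogeneity of mean 1 and variance 0.25, so shape 4), with mean 2 (range 1.5 to 2.5), and q = 0.25.

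For mean 2:

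- P(N=0) = (4/6)^4 = 0.198
- P(N=1) = 4 × (4/6)^4 × (2/6) = 0.263
- P(N≥1) = 0.802 and P(N≥2) = 0.539

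| Mean usable embryos | A, after failure only | A, all with surplus | B, and true first-transfer rate in both |
|---|---|---|---|
| 1.5 | 7.8% | 10.4% | 18.0% |
| 2.0 | 0.25 × 0.75 × 0.539 = 10.1% | 0.25 × 0.539 = 13.5% | 0.25 × 0.802 = 20.1% |
| 2.5 | 11.9% | 15.9% | 21.4% |

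With q also varied from 0.15 to 0.35, the A-to-B ratio for single transfers is 0.37 to 0.63 (after failure only) or 0.58 to 0.74 (all with surplus).

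Section 12.1 also permits two-embryo transfers. With mean 2 and frozen cycles after failure only, if half of transfers with two or more embryos available are double, the result is 8.9% v 25.1% (ratio 0.35). If all are double, an upper extreme, it is 6.3% v 30.2% (ratio 0.21).

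For clinical pregnancy at an assumed 35% per embryo with single transfers, B is 0.35 × 0.802 = 28.1%. A runs from 0.35 × 0.65 × 0.539 = 12.3% to 0.35 × 0.539 = 18.9%.

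**4. What a trial of 23 per group would show** (exact enumeration, two-sided Fisher test):

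| True A v B on this endpoint | B numerically higher | A numerically higher | p < 0.05 |
|---|---|---|---|
| 10.1% v 20.1% | 77% | 12% | 9% |
| 13.5% v 20.1% | 66% | 21% | 5% |
| 20.1% v 20.1% (no distortion) | 43% | 43% | 2.5% |

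In the two double-transfer cases, p < 0.05 occurs in 21% and 47% of trials.

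**5. Only women with a frozen cycle counted** (mean 2, single transfers, frozen cycle after failure only). About 23 × 0.75 × 0.539 = 9 Group A women contribute (7 to 11 over the range of means), or 12 (10 to 15) if all with surplus proceed, against about 18 (17 to 20) in B. The live birth rate per frozen cycle, A v B, depends on what else is assumed:

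- equal embryo potential: 25% v 25%, no bias
- second embryo at 70% of the first one's potential: 0.7 × 25% = 17.5% v 25%
- potential rising with embryo number: 27% v 26%

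**6. A second, simpler model as a cross-check.** Assume 85% reach a first transfer, every transfer has a 20% live birth rate, and 30% of Group A women with a failed fresh transfer have and use frozen embryos. Counting all randomised women, A = 0.85 × 0.80 × 0.30 × 0.20 = 4.1% and B = 0.85 × 0.20 = 17.0%. About 23 × 0.17 = 3.9 fresh-transfer births in A would go uncounted. With the live birth rate at 15% to 30% and the surplus share at 20% to 50%, A is 2.2% to 8.9% and B 12.8% to 25.5%. The direction is the same and the gap is wider.

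**The case against.** Read literally, intention to treat plus missing-as-negative gives all randomised women as the default denominator. That reading is reasonable, and treating the fresh-transfer delivery as not missing is itself an interpretation. Accepting the default does not rescue the endpoint, though: it scores that delivery as a failure, which is the distortion described.

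The Group A schedule in Table 1 has no frozen-cycle column, but this is weak evidence because the study-design figure is not available here. Sections 8.2 and 12.1 make the point without it.

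The magnitude is assumed, not taken from the plan. The two models differ more than twofold in Group A's central rate (10.1% and 4.1%). The 0.37 to 0.74 ratio and the low chance of significance hold only for single transfers. These limits stand. They affect the size, not the direction when all randomised women are counted.

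The consequence is also limited. This is a secondary endpoint in a 46-woman pilot, and cumulative live birth already counts fresh and frozen transfers. That leaves clinical pregnancy as the outcome with no fair comparison.

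**Conclusion.** The concern holds. The mismatch between groups follows from the plan's own text and needs no assumption. With all randomised women counted and equal performance per embryo, the endpoint is expected to be lower in Group A. Its size can only be illustrated: about 10% to 13% v 20% under single transfers with a mean of 2 usable embryos and 25% live birth per embryo, and wider with double transfers or fewer usable surplus embryos. Under single transfers most trials of this size would show no significant difference, so the main risk is a misleading numerical advantage for Group B. With only frozen-cycle women counted, no direction of bias can be claimed. The MII primary endpoint and cumulative live birth are not affected. This should be fixed, but it does not threaten the trial's main result.

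**What to change.** In the section 2 endpoint list and in section 8.2, define the endpoint as clinical pregnancy and live birth after the first embryo transfer (fresh in Group A, frozen in Group B), per randomised woman, with women who have no transfer counted as having no event. Keep cumulative live birth as the endpoint over all transfers. Report Group A frozen-cycle results descriptively, with their own stated denominator.

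If the listed endpoint cannot be changed, the smaller step is to label the first-frozen-cycle result descriptive, with no between-group test. That removes the misleading comparison but leaves the plan with no between-group comparison of clinical pregnancy.

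The main change alters a secondary endpoint of an authorised, registered trial, so it needs a protocol amendment and a matching registry update (the registry entry was not seen). It uses the hCG testing and the pregnancy and delivery data already planned in sections 13.1.6 and 13.1.4, and changes no treatment.
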